6.4.3 Recording of adverse events

Time period for collection of adverse events

Adverse Events will be collected from the time of signature of the informed consent throughout the treatment period and including the follow-up period, Visit 8.

SAEs will be recorded from the time of informed consent.

All bleeding events that fulfil the criteria of an AE, as judged by the investigator, should be reported using the standard procedures for assessing severity, causality and seriousness. Some bleeding events may not be considered as AEs if the situation is not different from that expected by the investigator (eg, usual blood loss during CABG).

Vascular events are assessed at each visit and may be reported by patients at anytime during the study. Non-serious vascular events will be reported as AEs. Any vascular events meeting the criteria for serious as outlined in section 6.4.2 will be reported.

Follow-up of unresolved adverse events

Any AEs that are unresolved at the patients last AE assessment at Visit 8 in the study are followed up by the investigator for as long as medically indicated, but without further recording in the CRF. AstraZeneca retains the right to request additional information for any subject with ongoing AE(s)/SAE(s) at the end of the study, if judged necessary.

Variables

The following variables will be collect for each AE;

- AE (verbatim)
- The date and time when the AE started and stopped
- Maximum intensity
- Whether the AE is serious or not
- Investigator causality rating against the Investigational Product (yes or no)
- Action taken with regard to investigational product
- AE caused subject's withdrawal from study (yes or no)
- Outcome

In addition, the following variables will be collected for SAEs:

- Date AE met criteria for serious AE
- Date Investigator became aware of serious AE
- AE is serious due to
- Date of hospitalisation
- Date of discharge
- Probable cause of death
- Date of death

34(60)

OF AN ELECTRONIC DOCUMENT.

A PRINTED COPY

5 H

THIS

PLEASE CHECK ITS VALIDITY BEFORE USE

- Autopsy performed
- Causality assessment in relation to Study procedure(s)
- Causality assessment in relation to Other medication
- Causality assessment in relation to Additional Study Drug
- Description of AE.

It is important to distinguish between serious and severe AEs. Severity is a measure of intensity whereas seriousness is defined by the criteria in Section 6.4.2. An AE of severe intensity need not necessarily be considered serious. For example, nausea that persists for several hours may be considered severe nausea, but not a SAE. On the other hand, a stroke that results in only a limited degree of disability may be considered a mild stroke but would be a SAE.

The intensity will be rated according to the following definition:

- Mild (awareness of sign or symptom, but easily tolerated);
- Moderate (discomfort sufficient to cause interference with normal activities);
- Severe (incapacitating, with inability to perform normal activities).

Causality collection

The Investigator will assess causal relationship between Investigational Product and each Adverse Event, and answer 'yes' or 'no' to the question 'Do you consider that there is a reasonable possibility that the event may have been caused by the investigational product?'

For SAEs causal relationship will also be assessed for other medication and study procedures. Note that for SAEs that could be associated with any study procedure the causal relationship is implied as 'yes'.

A guide to the interpretation of the causality question is found in Appendix B to the Clinical Study Protocol.

Adverse Events based on signs and symptoms

All AEs spontaneously reported by the subject or reported in response to the open question from the study personnel: 'Have you/the child had any health problems since the previous visit/you were last asked?' or revealed by observation will be collected and recorded in the CRF. When collecting AEs, the recording of diagnoses is preferred (when possible) to recording a list of signs and symptoms. However, if a diagnosis is known and there are other signs or symptoms that are

PRINTED COPY OF

IS A

THIS

AN ELECTRONIC DOCUMENT.

PLEASE CHECK ITS VALIDITY BEFORE USE

not generally part of the diagnosis, the diagnosis and each sign or symptom will be recorded separately.

Adverse Events based on examinations and tests

The results from protocol mandated vital signs will be summarised in the clinical study report. Deterioration as compared to baseline in protocol-mandated vital signs should therefore only be reported as AEs if they fulfil any of the SAE criteria or are the reason for discontinuation of treatment with the investigational product.

If deterioration in a vital sign is associated with clinical signs and symptoms, the sign or symptom will be reported as an AE and the associated vital sign will be considered as additional information. In the absence of clinical signs or symptoms, clinically relevant deteriorations in non-mandated parameters should be reported as AE(s).

Any new or aggravated clinically relevant abnormal medical finding at a physical examination as compared with the baseline assessment will be reported as an AE.

6.4.4 Reporting of serious adverse events

All SAEs have to be reported, whether or not considered causally related to the investigational product, or to the study procedure(s). All SAEs will be recorded in the CRF.

If any SAE occurs in the course of the study, then investigators or other site personnel inform appropriate AstraZeneca representatives within one day ie, immediately but **no later than the end of the next business day** of when he or she becomes aware of it.

The designated AstraZeneca representative works with the investigator to ensure that all the necessary information is provided to the AstraZeneca Patient Safety data entry site within one calendar day of initial receipt for fatal and life threatening events and within five calendar days of initial receipt for all other SAEs.

For fatal or life-threatening adverse events where important or relevant information is missing, active follow-up is undertaken immediately. Investigators or other site personnel inform AstraZeneca representatives of any follow-up information on a previously reported SAE within one calendar day ie, immediately but **no later than the end of the next business day** of when he or she becomes aware of it.

The Investigator or other study site personnel is to report a SAW to the appropriate AstraZeneca representative or delegate by telephone.

All SAEs have to be reported, whether or not considered causally related to the investigational product, or to the study procedure(s). All SAEs will be recorded in the CRF.

Clinical Study Protocol Drug Substance Ticagrelor Study Code D5130L00012 Edition Number 1

AN ELECTRONIC DOCUMENT. PLEASE CHECK ITS VALIDITY BEFORE USE

A PRINTED COPY OF

5 H

THIS

Investigators and other site personnel should inform (emergency report) appropriate AstraZeneca representatives of any SAE that occurs at his or her site in the course of the study within 1 day (in this section, within 1 day is defined as 'immediately but no later than the end of the next business day') of when he or she becomes aware of it (initial SAE report). This should apply whether or not the SAE is considered causally related to the study treatment or to the study procedure(s). The Principal Investigator should provide detailed information to AstraZeneca in writing within 4 calendar days of the initial report. The Principal Investigator should notify the serious adverse events in writing to the head of the study site immediately.

Follow-up information on SAEs should also be reported to AstraZeneca by the investigator(s) within the same time frames. If a non-serious AE becomes serious, this and other relevant follow-up information should also be provided to AstraZeneca within 1 day as described above.

The following information is required in the initial SAE report to AstraZeneca from the investigator(s); study code, site number, Enrolment code, adverse event, seriousness, start date. The following detailed information should be sent to AstraZeneca as soon as it becomes available;

Severity, outcome (including stop date, if available), causality (investigational product and if applicable any other concomitant drug), date when a non-serious AE became serious, withdrawal of study treatment, treatment of adverse event, concurrent therapy (except for treatment of AE), concurrent medication (including pre-study medication if the causality of the AE cannot be assessed), date of birth, sex, other current illnesses, relevant medical history and if applicable, date and course of death.

In addition AstraZeneca will provide details of any *unexpected* serious adverse drug reactions reported with regard to the test product in this study to the Head of the study site, Principal Investigator and the regulatory agency. The Head of the study site should submit a written report to the IRB providing the details of all adverse event case(s) reported by AstraZeneca.

6.4.5 Reporting of suspected vascular events as adverse events

Non-serious suspected vascular events are reported as AEs. They are part of the natural history of the condition under investigation and therefore may be expected.

Once an event has been identified, using their clinical judgement, investigators must determine if the event is an acute vascular event (including the clinical terms for ACS, MI, UA, etc). All events will be recorded in the eCRF.

6.4.6 Bleeding assessments

For all bleeding events, the investigator will complete information on the eCRF specific to that bleeding event, including classification of the event as described in Section 6.4.6.1 below and a determination of whether it is an AE.

Approved

Date Printed:

6.4.6.1 Definition of bleeding events

Bleeding events will be classified as shown below:

For patients experiencing a bleeding event that fulfils criteria in more than one category, the event will be assigned to the most severe category. This classification is a modification of the CURE definitions (Jneid H et al 2003).

Major bleed – fatal/life threatening

Any one of the following:

- Fatal
- Intracranial
- Intrapericardial bleed with cardiac tamponade
- Hypovolemic shock or severe hypotension due to bleeding and requiring pressors or surgery
- Clinically overt or apparent bleeding associated with a decrease in Hb of more than 50 g/L^a (3.1 mmol/L^b; 0.775 mmol/L^c)^d
- Transfusion of 4 or more units (whole blood or packed red blood cells [PRBCs]) for bleeding.

Major bleed- other

Any one of the following:

- Significantly disabling (eg, intra-ocular with permanent vision loss)
- Clinically overt or apparent bleeding associated with a decrease in Hb 30 g/L^a (3.1 mmol/L^b; 0.465 mmol/L^c)d to 50 g/L^a (3.1 mmol/L^b; 0.775 mmol/L^c)^d
- Transfusion of 2 to 3 units (whole blood or PRBC) for bleeding.

Minor bleed

Requires medical intervention to stop or treat bleeding (eg, epistaxis requiring visit to medical facility for packing).

Minimal bleed

All others (eg, bruising, bleeding gums, oozing from injection sites, etc) not requiring intervention or treatment.

Definitions of Terms

a Reference range 130 to 180 g/L (males); 120 to 160 g/L (females).

38(60)

IS A PRINTED COPY OF AN ELECTRONIC DOCUMENT. PLEASE CHECK ITS VALIDITY BEFORE USE

THIS

- b Reference range Hb tetramer 8.1 to 11.2 mmol/L (males); 7.4 to 9.9 mmol/L (females).
- c Reference range Hb monomer 2.02 to 2.80 mmol/L (males); 1.85 to 2.47 mmol/L (females).
- d To account for transfusions, Hb measurements will be adjusted for any PRBCs or whole blood given between 2 blood measurements. A transfusion of one unit of blood will be assumed to result in an increase of 10 g/La; 0.62 mmol/Lb; 0.155 mmol/Lc in Hb. Therefore, to calculate the true change in Hb if there has been an intervening transfusion between 2 blood measurements, the following calculations should be performed: Δ Hb = [baseline Hb – post-transfusion Hb] + [number of transfused units x conversion factor in Hbe].
- e Conversion factor = 10 g/La; 0.62 mmol/Lb; 0.155 mmol/Lc.

All blood product transfusions during the study will be recorded in the eCRF. In addition, all haemoglobin (haematocrit) values obtained in the 7 days preceding, during and for 7 days after a bleeding event will be recorded in the eCRF. Bleeding event data will be collected in sufficient detail so that categorisation according to other previously published scales (eg, TIMI) will be possible.

Information regarding the relationship of any bleed (excluding minimal) will be recorded on the eCRF.

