4.2 Exclusion criteria

Subjects are not to enter the study if any of the following exclusion criteria are fulfilled:

- Any indication for oral anticoagulant (e.g., atrial fibrillation, mitral stenosis or prosthetic heart valve) or dual antiplatelet treatment (e.g., clopidogrel, prasugrel, ASA dose other than 75 to 100 mg daily) during study period
- 2. Concomitant therapy with strong CYP3A inhibitors, CYP3A substrates with narrow therapeutic index, or strong CYP3A inducers within 14 days and during study treatment and during:
 - Strong inhibitors: ketoconazole, itraconazole, voriconazole, telithromycin, clarithromycin, nefazadone, ritonavir, saquinavir, nelfinavir, indinavir, atanazavir.
 - Substrates with narrow therapeutic index: cyclosporine, quinidine.
 - Strong inducers: rifampin/rifampicin, phenytoin, carbamazepine.

- The sponsor should be consulted for enrolment with any concomitant medicines which are suspected of undergoing strong drug-drug interaction

- 3. Increased bleeding risk including:
 - Recent (within 30 days) GI bleeding
 - Any history of intracranial, intraocular, retroperitoneal, or spinal bleeding
 - Recent (within 30 days of dosing) major trauma
 - Sustained uncontrolled hypertension (systolic blood pressure [SBP]>180mmHg or diastolic blood pressure [DBP]>100mmHg)
 - History of hemorrhagic disorders that can increase the risk of bleeding, e.g., haemophilia, von Willebrand's disease.

Approved

Date

_	Inability to discontinue required concomitant therapy with non-steroidal
	anti-inflammatory drug (NSAID) at screening

- Patients that have used within 30 days of screening, any oral or parenteral antithrombotic agent (Section 5.5)
- Platelet count less than 100,000 mm³ or hemoglobin <10 g/dL
- 4. Diabetic patients with HbA1c \geq 10%
- 5. Contraindication or other reason that clopidogrel, ASA, or ticagrelor should not be administered (e.g., hypersensitivity, active bleeding, major surgery within 30 days of dosing, any bleeding tendency [coagulation defects], acute or chronic liver disease etc.)
- 6. History of drug addiction or alcohol abuse in the previous 2 years
- 7. Patient requires dialysis
- 8. Participation in another investigational drug or device study within 30 days of dosing
- 9. Recent (within 30 days of dosing) blood donation
- 10. Patients that are scheduled for revascularization (e.g., PCI, CABG) during the study period

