13.1 Major bleeding events

Major bleeding events should be managed according to accepted standard of care.

If a patient experiences a major bleed as defined in Section 6.4.6.1, study drug should usually be discontinued but may be resumed at the discretion of the investigator provided the cause of bleeding has been identified and controlled.

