13.2 Minor bleeding events

If a patient experiences a minor bleeding event as defined in Section 6.4.6.1, study drug may be continued, interrupted temporarily or discontinued permanently at the discretion of the investigator.

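### The haemoglobin criterion for 'Major bleed – other' gives 30 g/L as 3.1 mmol/L in the tetramer unit; the protocol's own conversion factor gives 1.86 mmol/L

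*Protocol*

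**What the plan says.** Section 6.4.6 has the investigator record, for every bleeding event, a "classification of the event as described in Section 6.4.6.1 below". In Section 6.4.6.1 one of the criteria for 'Major bleed – other' is overt bleeding with a "decrease in Hb 30 g/L^a (3.1 mmol/L^b; 0.465 mmol/L^c)d to 50 g/L^a (3.1 mmol/L^b; 0.775 mmol/L^c)^d". The superscripts denote three units: a is g/L, b is mmol/L of the haemoglobin tetramer, and c is mmol/L of the monomer. The more severe category, fatal or life-threatening, uses a fall of more than 50 g/L, given as 3.1 mmol/L in unit b and 0.775 mmol/L in unit c.

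Footnote e gives the link between the units: "Conversion factor = 10 g/La; 0.62 mmol/Lb; 0.155 mmol/Lc". Footnote d uses the same three values as the assumed rise per transfused unit of blood.

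The category affects dosing. After a major bleed, Section 13.1 says "study drug should usually be discontinued but may be resumed at the discretion of the investigator", once the cause has been found and controlled. After a minor bleed, Section 13.2 says "study drug may be continued, interrupted temporarily or discontinued permanently at the discretion of the investigator".

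**The concern.** Two limits that are 20 g/L apart cannot both equal 3.1 mmol/L in the same unit. The three units are printed as equivalents, and nothing says that g/L prevails if they disagree.

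Read in unit b, the criterion runs from 3.1 to 3.1 mmol/L. Anything above 3.1 already belongs to the fatal or life-threatening category, so the haemoglobin criterion for 'Major bleed – other' is met only at exactly 3.1 mmol/L. A fall between the true lower limit and 3.1 mmol/L, in a patient with no disabling bleed and fewer than 2 units transfused, would drop to minor or minimal. The default of stopping study drug would then be lost, so the error works in the less cautious direction.

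**Working it through.** **Inputs, all from Section 6.4.6.1**

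- Factor (footnotes d and e): 10 g/L = 0.62 mmol/L (b) = 0.155 mmol/L (c).
- Printed lower limit: 30 g/L = 3.1 (b) = 0.465 (c).
- Printed upper limit: 50 g/L = 3.1 (b) = 0.775 (c).
- Reference range in g/L (footnote a): 130 to 180 for males, 120 to 160 for females.
- Footnote b: "Reference range Hb tetramer 8.1 to 11.2 mmol/L (males); 7.4 to 9.9 mmol/L (females").

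**Formula.** Value in unit b = (g/L ÷ 10) × 0.62. Value in unit c = (g/L ÷ 10) × 0.155.

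**Step 1: conversion of the limits**

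| Limit | Unit b, computed | Unit b, printed | Unit c, computed | Unit c, printed |
|---|---|---|---|---|
| 50 g/L | 5 × 0.62 = 3.10 | 3.1 | 5 × 0.155 = 0.775 | 0.775 |
| 30 g/L | 3 × 0.62 = **1.86** | **3.1** | 3 × 0.155 = 0.465 | 0.465 |

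Three of the four figures reproduce exactly. The unit-b figure for 30 g/L does not. Converted back, 3.1 ÷ 0.62 × 10 = 50 g/L.

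**Step 2: ratio of the two molar units.** By the factor, b/c = 0.62 ÷ 0.155 = 4.0. At the upper limit, 3.1 ÷ 0.775 = 4.0. At the printed lower limit, 3.1 ÷ 0.465 = 6.67. With 1.86 the ratio is 1.86 ÷ 0.465 = 4.0 again.

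**Step 3: could a different factor be intended?** Footnote b allows a test that does not use the bleeding limits.

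| Reference limit | × 0.62 per 10 g/L | Printed in unit b |
|---|---|---|
| 130 g/L | 8.06 | 8.1 |
| 180 g/L | 11.16 | 11.2 |
| 120 g/L | 7.44 | 7.4 |
| 160 g/L | 9.92 | 9.9 |

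All four agree after rounding. If 30 g/L really were 3.1 mmol/L, the factor would be 3.1 ÷ 3 = 1.033 per 10 g/L. The male lower limit would then be 13 × 1.033 = 13.4 mmol/L, above the printed male upper limit of 11.2. So the factor stands and the figure is wrong.

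**Step 4: size.** 3.10 − 1.86 = 1.24 mmol/L, and 1.24 ÷ 0.62 × 10 = 20 g/L. The falls affected are 30 to just under 50 g/L, which is 1.86 to just under 3.1 mmol/L.

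**The case against.** The misprint itself is hard to defend; the case on the other side is that it does not matter.

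- **It corrects itself on the page.** The line opens with 30 g/L, the monomer value is right, and the factor stands below. A fall of 40 g/L (4 × 0.62 = 2.48 mmol/L) still meets the criterion in g/L, and a range from 3.1 to 3.1 is visibly odd. This stands: misclassification needs someone to work in unit b alone. It does not make the printed limit right.
- **Exposure is slight.** About 34 patients are planned, at US sites, with 7 to 9 days on each drug. The eligibility limit is in conventional units ("hemoglobin <10 g/dL"), and Table 1 schedules laboratory tests at Visit 1 only, so a fall would appear only on unscheduled testing. This stands, although the unit for reporting haemoglobin around a bleed is not stated.
- **No stated analysis uses it.** The safety outcome variables are adverse events, physical examination and vital signs, and Section 12.2 describes no summary by bleeding category. Haemoglobin "values obtained in the 7 days preceding, during and for 7 days after a bleeding event will be recorded in the eCRF", so events could be reclassified. This stands for reporting. Later reclassification cannot undo a dosing decision already taken.
- **The investigator may stop the drug anyway.** Section 13.2 allows this, and Section 5.7 allows discontinuation for safety. This stands; what is lost is the default, not the option.
- **Other conversions do not match exactly either.** In footnote c, 180, 120 and 160 g/L give 2.79, 1.86 and 2.48 by the factor, against 2.80, 1.85 and 2.47 printed. These are rounding: footnote b divided by 4 gives 11.2 ÷ 4 = 2.80, 7.4 ÷ 4 = 1.85 and 9.9 ÷ 4 = 2.475. Differences of 0.01 mmol/L are of another order than an error of 1.24 mmol/L.

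**Conclusion.** The point holds and is minor. The tetramer-unit equivalent of the 30 g/L limit should be 1.86 mmol/L; the printed 3.1 mmol/L is the 50 g/L value and is too high by 1.24 mmol/L (20 g/L). This rests only on the conversion factor in the same section, confirmed by the monomer values and the tetramer reference ranges.

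The consequence is conditional. It arises only if the criterion is read in unit b, for a fall of 30 to just under 50 g/L, with no disabling bleed and fewer than 2 units transfused. That US sites will seldom read haemoglobin in mmol/L is an assumption, though a likely one. The g/L and monomer limits, the 50 g/L tetramer value, and the disability and transfusion criteria are unaffected. So are the platelet reactivity analysis and the sample size. It is still worth correcting, because investigators apply this rule to every bleed and it sets the default for stopping study drug.

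**What to change.** In Section 6.4.6.1, under 'Major bleed – other', change the first 3.1 mmol/L to 1.86 mmol/L, so that the limits read 30 g/L (1.86; 0.465 mmol/L) to 50 g/L (3.1; 0.775 mmol/L). Check the bleeding form in the eCRF, whose content is not shown, and correct it only if it carries the same figure. The cost is one figure in the protocol; no data collection, analysis or sample size changes.

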6.4.7 Laboratory safety assessment

Blood and urine samples for determination of clinical chemistry, haematology, and urinalysis will be taken at the times indicated in the Study Plan (see Table 1)

The following laboratory variables will be measured:

Clinical chemistry (Serum)	Haematology (Whole Blood)	Urinalysis
Creatinine	Haemoglobin	Glucose
Alkaline phosphatase	Haematocrit	Haemoglobin
Aspartate aminotransferase	Platelet Count	Protein
(AST)	White blood cells	
Alanine aminotransferase (ALT)	Erythrocytes (RBCs)	
Total Bilirubin	••••	
Blood Urea Nitrogen (BUN)		
Glucose		
Total Protein		
Albumin		
Sodium		
Potassium		
Bicarbonate		
Phosphate		
Chloride		
Pregnancy		

For blood volume see Section 7.1.

Approved

Da

6.4.8 Physical examination

Refer to Study Plan, Table 1 for the visits when a physical exam will be performed.

Medically qualified individual will perform a physical examination and include an assessment of the following: general appearance, skin, head and neck, lymph nodes, thyroid, musculoskeletal/extremities, cardiovascular, lungs, abdomen, and neurological systems.

The targeted examination will be performed by medically qualified individuals and include skin, cardiovascular, lung, abdomen, and neurological evaluations.

Results will be recorded in the eCRF as an overall normal or abnormal with a listing of abnormalities.

